## 3. STUDY DESIGN

Diagnostic prospective cohort study: mass screening through conventional symptoms screening by a doctor, a physical exam and with testing of CAD4TB® and AeoNose™ as well as bacteriological testing of presumptive cases.

An estimated 5000 individuals will be invited to participate. All prisoners and employees will be eligible for inclusion. The sample size is based on an estimated incidence of 3000-5000/100.000 and a presumptive number of 150-250 active TB cases to be found in order to have enough cases to first train the neural network (with at least 500 - 1000 healthy individuals and a 100 active TB cases) and then perform the blind predictions on the rest of the participants to establish sensitivity and specificity of the AeoNose™.

The study consists of one primary visit and, in case of suspicion of presumptive TB but no confirmed TB or alternative diagnosis, two follow-up visits after three and six months respectively. The estimated total study duration will be from February 2020 to May 2021. The study settingwill be the Buen Pastor, Esperanza and Tacumbú prisons in Asunción, Paraguay Required condition to perform the study in each of these three institutions is safety for the study team and also the guards and prisoners. In case of unstable conditions we will look for an alternative penal institution.

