#### Visit 1.

- 1. Participants will watch an animation (video) with voice-over in Spanish, Guarani or Portuguese with general information on TB and an explanation of the study procedures. Each participant will be offered to be tested voluntarily for HIV by PRONASIDA. An independent volunteer witness is present in the room to guarantee that the participant has understood the information correctly and is able to ask questions if necessary. Participants may then decide to sign informed consent using signature or fingerprint. Individuals can also decline participation, or take time to consider their participation and return later.
- 2. After providing informed consent, a study nurse will take vital signs (blood pressure, pulse and axillary temperature) and measure the participants weight, height, temperature, middle upper arm circumference, as well as ask for smoking habits, alcohol and/or drug. Co-morbidities, medication and food intake (4 hours prior to testing) will be recorded in the digital case record form. If the participant agrees a HIV rapid test will be performed using a finger prick blood sample. Participants with a positive result will be notified and referred to the national HIV program (PRONASIDA) for final diagnosis and treatment according to national HIV guidelines.
- At the third station, a technician will perform the CXR and will process the digital image with CAD4TB™ software. A TB likelihood output score is presented within minutes.
- At the fourth station, a technician will take a breath sample with an AeoNose™ device during 5 minutes in a room free of gasses and odours.
- 5. At the fifth station, a doctor will first take a history of symptoms and will then examine the participant for signs of TB:
  - o Healthy / ill
  - Cough (15 days or longer)
  - Sputum or haemoptysis
  - Weight loss
  - Fever (continuous or intermittent)
  - Night sweats
  - o Chest pain

- Dyspnea / shortness of breath
- o Loss of appetite
- o Lymphadenopathy
- Pulmonary auscultation
- Abdominal distension
- Anaemic conjunctivae

Also the dental status of the participants will be assessed.

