The digital CXR image will be analysed by CAD4TB® and the doctor will interprete the CAD4TB® output score and check the CXR for alternative diagnosis. All the findings by the study doctor will be recorded in the digital case record form. At the end of this visit the doctor will decide on health status of the participant: either the participant is considered healthy or a presumptive TB case.

For healthy participants the study ends after this 5th station.

- 6. Presumptive TB cases (see 6.1.1 Case definitions) will be asked to produce two sputum samples outside, preferably in the open air. Sputum can be either be produced spontaneously or via sputum induction with nebulized saline. Saline solution will be nebulized using a portable nebulizer. Sputum samples can deposited in standard containers. Samples will be stored in a cool box and transported to the laboratory the same day. Samples will then be processed and analysed by the National Reference Laboratory, Laboratory San Alfonso and IICS using GeneXpert® molecular testing and MGIT mycobacterial culture.
- 7. All participants will be educated about the importance of seeking medical care if symptoms compatible with TB emerge at any time.
- 8. In case a participant is passively identified with TB during the study period by the prison health services or PNCT, the study researchers will be notified. Clinical and microbiological data will be shared based on informed consent given by the participant.

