#### 4.3 Sample size calculation

Based on WHO definitions, mass screening includes every person in a vulnerable community. The combined prisons of Tacumbú, Esperanza, Buen Pastor house around 4700 PPL. An additional 500 employees (estimated number, to be confirmed) who are in direct contact with the PPL will also be included. Based on calculations we expect to detect around 200-240 cases of active tuberculosis in prisoners (3-6% of 4000 PPL) and 0-5 cases in employees (estimated 0.2% of 1000 employees). The number of expected cases in the latter group could be an underestimation as these people are in constant contact with PPL and have a higher risk than the general population of active TB.

The study sample size is based on the need for at least 100 cases with active TB to build a robust AeoNose™ neural network (calibration model) and subsequently another 100-150 cases to make a blind prediction (validation model). A systematic literature review of acceptability of TB screening among risk groups showed an average percentage of screening consent of 72% among prisoners. (range 18-100%, Mitchell et al. 2012)

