#### 8.1 Primary study parameter(s)

Primary study parameters are the number of TB cases cases by CAD4TB® CXR analysis and AeoNose™ breath sampling.

A binary assessment of the presence or absence of illness has four possible outcomes: true positives (TP), false positives (FP), true negatives (TN) and false negatives (FN). The relationship of the four outcomes is the basis of sensitivity and specificity analysis which determines the accuracy and predictive value of a diagnostic tool.

*True positive:* A positive test result in a confirmed TB case.

*False positive*: A positive test result with negative sputum results and no confirmed TB during follow-up.

*True negative*: A negative test result with no confirmed TB during follow-up. *False negative*: A negative test result with confirmed TB during follow-up.

Receiver operating characteristics (ROC) will be generated using an ROC package, and bootstrapping to generate confidence intervals in the ROC plot. T-testing or McNemar's test will be used to compute P values when comparing the sensitivity of conventional screening and CAD4TB® and AeoNose™ at assumed levels of specificity. We will also use multivariate analysis to analyse influences of different combinations of participant characteristics.

CAD4TB®: The collection of digital CXR images will be analysed and compared to presumptive and confirmed cases. The number of true/false positives and negatives will be used to calculate sensitivity and specificity as described above. The predictive value of the test will be analysed.

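### Section 8.1 compares conventional screening with CAD4TB, but nothing requires the doctor's symptom/sign judgement to be recorded before the CAD4TB score is seen (minor)

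*Protocol*

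**What the plan says.** **The comparison.** Protocol section 8.1: "T-testing or McNemar's test will be used to compute P values when comparing the sensitivity of conventional screening and" CAD4TB and AeoNose, at assumed levels of specificity. Section 8 sets a two-sided 0.05 level for all comparisons.

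**What conventional screening means.** Section 8.1 does not say. The nearest wording is in section 3, which describes "mass screening through conventional symptoms screening by a doctor, a physical exam and with testing of" CAD4TB and AeoNose. That wording lists the doctor's work apart from the two index tests but gives no positivity rule. Section 6.1.1 contains two results that do not use CAD4TB: the doctor's judgement that symptoms or signs suggest TB (the first part of the presumptive-TB definition), and the respiratory-symptomatic rule (cough or phlegm for more than 14 days). Section 8.1 refers to neither.

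**Order of events at Visit 1.**
- Third station, radiograph: "A TB likelihood output score is presented within minutes". Section 6.2 adds that the score is presented to the doctor, who also reads the radiograph during the consultation.
- Fifth station: "a doctor will first take a history of symptoms and will then examine the participant for signs of TB".
- The text then turns to interpreting the score and checking the radiograph, followed by "All the findings by the study doctor will be recorded in the digital case record form".
- Finally: "At the end of this visit the doctor will decide on health status of the participant", that is, healthy or presumptive TB.

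Sections 6.3 and 10.1 say that data are entered immediately.

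**The concern.** A paired comparison of two screens is informative only if each result is formed without knowledge of the other. Here the doctor can have the CAD4TB score before committing to a view on symptoms and signs. A high score may prompt a doctor to call borderline symptoms suggestive, and a low score may do the opposite. Either way the two results are pulled into agreement and the measured difference shrinks.

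The AeoNose comparison uses the same conventional result. Breath signals are sent for analysis later (section 6.2), so they cannot influence the doctor. That comparison would still inherit any shift caused by the CAD4TB score.

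An analysis plan can choose the comparator later. It cannot recover an unprompted judgement that was never recorded. That part of the problem lies in data collection, which this protocol describes.

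**Working it through.** **1. Is a CAD4TB-free judgement secured?** Four parts of the text bear on this.
- Visit 1, fifth station: the words on order place history before examination. They do not place either before display of the score.
- The next paragraph of Visit 1 mentions score interpretation after history and examination. This suggests an order but does not require one.
- Sections 6.3 and 10.1 require immediate entry. They do not require entry before the score is displayed.
- The overall TB decision comes at the end of the visit. Under section 6.1.1 a score above the threshold is sufficient for presumptive TB, so this decision contains the score.

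The order is therefore suggested but not required.

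**2. Why the end-of-visit decision cannot be the comparator.** If it were, every TB case above the CAD4TB threshold would be comparator-positive by definition. The cell for CAD4TB-positive, conventional-negative cases would be 0, and CAD4TB could never appear more sensitive.

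**3. Denominator.** Section 3 expects 150-250 cases among 5000 people at 3000-5000 per 100,000. Check: 5000 × 0.03 = 150 and 5000 × 0.05 = 250, so the figure reproduces. Section 4.3 gives 200-240 from 3-6% of 4000, but 4000 × 0.03 = 120 and 4000 × 0.06 = 240. The section 3 range is used here because it agrees with its own inputs.

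**4. Shift per changed case.** Each case whose conventional result changes moves conventional sensitivity by 100/N percentage points.
- Section 3 range: 100/250 = 0.40 and 100/150 = 0.67.
- AeoNose validation set, "another 100-150 cases to make a blind prediction (validation model" in section 4.3: 100/150 = 0.67 and 100/100 = 1.00.

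**5. Illustration of the gap (assumed inputs).** Take CAD4TB sensitivity 0.95, a prior result cited in section 1 and not a planning value. Assume a true symptom/sign sensitivity s, independent errors within cases, and a share k of symptom-negative, CAD4TB-positive cases that turn positive because the score was seen. Then apparent sensitivity = s + 0.95 × (1 − s) × k.
- s = 0.70, k = 0: gap 0.95 − 0.70 = 0.25.
- s = 0.70, k = 0.50: 0.70 + 0.95 × 0.30 × 0.50 = 0.843, gap 0.107.
- s = 0.50, k = 0.50: the gap falls from 0.45 to 0.21.
- s = 0.80, k = 0.50: the gap falls from 0.15 to 0.055.

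**6. Illustration of the test (assumed discordant counts).** Take 200 cases, the midpoint of 150-250. Let b be cases positive on CAD4TB only and c cases positive on symptoms/signs only. The gap is (b − c)/200, and p is the exact two-sided McNemar value (binomial on b + c pairs with probability 0.5).

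| Scenario | b | c | Gap (points) | p |
|---|---|---|---|---|
| No influence | 40 | 20 | 10.0 | 0.0135 |
| Five CAD4TB-only cases changed | 35 | 20 | 7.5 | 0.058 |
| A quarter of both kinds pulled to agreement | 30 | 15 | 7.5 | 0.036 |
| Larger gap, no influence | 60 | 20 | 20.0 | <0.0001 |
| Larger gap, half of both kinds pulled | 30 | 10 | 10.0 | 0.002 |

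Depending on the assumed counts, the conclusion may change, or it may survive with the estimate halved.

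**7. Choice of test.** Each participant has two yes/no results, so the data are paired and binary. McNemar's test applies and a t-test does not.

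**The case against.** The strongest reply has four parts.

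- **Section 3 already says what conventional screening is, and the positivity rule can wait for the analysis plan.** This largely stands. A reader might infer that the comparator is undefined, or that the end-of-visit decision is the planned comparator. The documents support neither: section 3 points to symptoms and examination, and no sentence proposes the end-of-visit decision. What remains is that 8.1 makes no link to a recorded result.
- **The described flow already puts symptoms first.** History and examination precede score interpretation in the text, and sections 6.3 and 10.1 call for immediate entry. A reader might infer from the recording sentence in Visit 1 that findings are entered only after the score. That goes too far, because the immediate-entry sentences point the other way. They still do not require entry before the score is seen, while section 6.2 presents the score to the doctor.
- **The case record form (Annex IV) is not shown and may already separate the fields.** This is fair. The gap lies in what the protocol requires; practice on site may be better.
- **The comparison is peripheral.** This stands. It appears in no objective (section 2) and no endpoint (sections 6.1.2 and 6.1.3). The sensitivity and specificity of AeoNose and CAD4TB use the machine outputs as index results and are not shown to be harmed.

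**Conclusion.** The point holds as a minor one. The protocol plans to test conventional screening against CAD4TB without requiring that the conventional result be committed before the doctor sees the score, and an analysis plan written later cannot repair that.

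The direction of concern is toward a smaller measured difference, on the assumption that influence acts toward agreement. Its size cannot be estimated from the documents. The arithmetic result is 0.40 to 0.67 points per changed case over 150-250 cases. The gaps and p-values in the illustrations rest on assumed symptom/sign sensitivity, assumed influence and assumed discordant counts.

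A reader might infer that the comparison is already biased, or that significance will be lost. The documents do not show that any judgement will be influenced, and with a larger true gap the conclusion would survive.

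**What to change.** **In section 8.1:**
- Define conventional screening as the symptom/sign judgement in the first part of the section 6.1.1 presumptive-TB definition, alone. State that it is not the end-of-visit healthy/presumptive decision.
- Delete the t-test and name McNemar's test only.
- Use the respiratory-symptomatic rule, applied to the symptom items recorded under section 6.1.4, only as a sensitivity analysis. It covers cough and phlegm alone, so it is narrower than what section 3 describes. The same doctor elicits those items, so it is less exposed to the score but not immune.

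**In the Visit 1 procedure and the eCRF:** record and lock that judgement after history and examination and before the CAD4TB score, heatmap and radiograph are shown to the doctor. The presumptive-TB decision continues to use all information as now.

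**Cost:** one reworded sentence in 8.1, one extra eCRF field, a later display of the score and images within the same consultation, and brief staff instruction. Consultations may run slightly longer. Participants have no extra visits or procedures.

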CAD4TB®: CAD4TB® has been widely adopted over the past years, currently analyzing over 5000 CXR every day in clinics all over the world, including in prison facilities. The CAD4TB® software is going through continuous improvements. In a systematic review of CAD for detection of tuberculosis, version 1 and 3 of the software achieved AUC of 0.71-0.87 for sputum confirmed cases. (Pande, Int J TB Lung Dis. 2016) Version 5 of the software demonstrated an AUC of 0.90 in 47510 images with the clinical decision to treat as reference. (Melendez, Int J TB Lung Dis. 2018) Sensitivity and specificity is dependent on the selected threshold score. Threshold scores achieving high sensitivity (≥95%) can be reached with moderate-to-high specificity, performing similarly to expert radiologists. Version 6 of CAD4TB® was released in 2018. In a validation data set of 5665 CXR images the software attained an AUC of 0.987 for radiological reference and 0.885 for bacteriological reference (Murphy et al. Arxiv pre-print March 2019). CAD4TB® has already been tested as a triage tool to select presumptive TB cases for GeneXpert® testing. In a study in 388 South African presumptive TB cases, pre-screening with CAD4TB® version 3 led to an almost 50% reduction in cost per screened subject and cost per notified TB case, and more than doubled the number of subjects screened per day, at the expense of only a small number of missed cases. (Philipsen, Sci Rep 2015) These benefits were realized by guickly identifying TB negative subjects and reducing the total number of expensive and time-consuming NAAT tests.

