## 6. METHODS

## 6.1 Study parameters/endpoint

6.1.1 Case definitions: Presumptive TB: Any participant with symptoms or signs suggestive of TB as judged by the study doctor.

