## Respiratory symptomatic

Any participant presenting with cough or phlegm of duration of more than 14 days.

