## 8. STATISTICAL ANALYSIS

All data will be analysed using SPSS software. (IBM, United States) The data of the participants will be analysed cross-sectional. Follow-up of participants with presumptive TB but negative microbiological testing will be completed until 6 months after Visit 1. After a

follow up period of 6 months a final diagnosis will be made (either healthy or TB case and the participant will be offered treatment if indicated). A p-value (two-sided) < 0.05 is considered to indicate a statistically significant difference in all comparisons. Multivariate analysis will be performed to analyse influences of different combinations of participant characteristics.

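### Section 8.1 compares sensitivities at assumed specificity levels, but conventional screening is a yes/no result whose specificity can only be observed, so the paired test may compare tools at different false-positive rates

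*Protocol*

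**What the plan says.** Section 8.1 (Primary study parameter(s)) plans ROC curves with bootstrap confidence intervals. On testing, it states that "T-testing or McNemar's test will be used to compute P values". The contrast to be tested is described there as "comparing the sensitivity of conventional screening and CAD4TB ® and AeoNose ™ at assumed levels of specificity". Section 8 adds that "A p-value (two-sided) < 0.05 is considered to indicate a statistically significant difference in all comparisons". Section 8.1 gives no specificity level and does not define conventional screening.

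The nearest description is in Section 3: "mass screening through conventional symptoms screening by a doctor, a physical exam". The case definitions in Section 6.1.1 contain two symptom-based entries, both yes/no. One is the first limb of presumptive TB, "Any participant with symptoms or signs suggestive of TB as judged by the study doctor". The other is the respiratory symptomatic category, "Any participant presenting with cough or phlegm of duration of more than 14 days".

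The devices differ in kind. Section 5.1 describes the CAD4TB output as a score from 0 to 100, and Section 6.1.1 leaves its threshold to be determined. The AeoNose paragraph of Section 8.1 describes a similarity value whose chosen threshold sets the balance of outcomes. Section 5.2 says of CAD4TB: "Sensitivity and specificity is dependent on the selected threshold score".

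**The concern.** A test with a continuous output can be moved along its ROC curve to any chosen specificity. A yes/no judgement is one point in ROC space: it has the specificity that the data show, and its sensitivity cannot be read off at another level. The stated rule therefore cannot be applied to one of the three tools being compared.

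If the devices are read at an assumed level while conventional screening stays at its own specificity, a paired test in TB cases sets sensitivities against each other at unequal false-positive rates. McNemar's test in cases sees only sensitivity, so nothing in it corrects for the mismatch. A significant result could reflect where the threshold was put and yet be reported as a device finding more, or less, TB than symptom screening. Section 8.1 names no other test of the devices against conventional screening.

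**Working it through.** **Plan's own figure.** The protocol gives no expected sensitivity, specificity level or power for this comparison, so there is nothing to reproduce. The related case count does reproduce: 5000 × 0.03 = 150 and 5000 × 0.05 = 250 TB cases (Section 3).

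**Inputs from the protocol**
- CAD4TB version 6, bacteriological reference: AUC 0.885 (Section 5.2).
- CAD4TB version 6: sensitivity 95%, specificity 70% (Section 1; reference standard for this pair not stated).
- AeoNose, hospital-admission study: sensitivity 85–93%, specificity 63–73% (Section 5.2). I pair the two lower ends, 85% with 63%.
- TB cases: 150–250 overall (Section 3), 100–150 for AeoNose validation (Section 4.3).

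**Assumptions.** The ROC curves are equal-variance binormal. The accuracy of conventional screening is not in the documents, so its values below are assumed.

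**Formulae.** Separation d = √2 × z(AUC), or d = z(Se) + z(Sp) from a known pair. Sensitivity at specificity Sp is Φ(d − z(Sp)). The device equals a conventional sensitivity Se_c at Sp* = Φ(d − z(Se_c)).

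**Step 1: device sensitivity by assumed level**
- CAD4TB, AUC 0.885: d = 1.414 × 1.200 = 1.698. At 70%: Φ(1.698 − 0.524) = 88.0%. At 90%: Φ(1.698 − 1.282) = 66.1%.
- CAD4TB, 95%/70%: d = 1.645 + 0.524 = 2.169.
- AeoNose, 85%/63%: d = 1.036 + 0.332 = 1.368.

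| Assumed specificity | CAD4TB, AUC 0.885 | CAD4TB, 95%/70% | AeoNose, 85%/63% |
|---|---|---|---|
| 70% | 88.0% | 95.0% | 80.1% |
| 80% | 80.4% | 90.8% | 70.1% |
| 90% | 66.1% | 81.3% | 53.5% |
| 95% | 52.1% | 70.0% | 39.1% |

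Moving the level from 70% to 90% shifts CAD4TB sensitivity by 88.0 − 66.1 = 21.9 points (AUC input) or 95.0 − 81.3 = 13.7 points (95%/70% input), with no change in the device. Conventional sensitivity stays where it is.

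**Step 2: where the sign would change**
- Se_c = 75%, AUC 0.885: Sp* = Φ(1.698 − 0.674) = 84.7%.
- Se_c = 75%, 95%/70%: Sp* = Φ(2.169 − 0.674) = about 93%. At the 90% level CAD4TB is still 81.3 − 75 = 6.3 points ahead.
- Over Se_c from 40% to 90%, Sp* runs from 97.4% down to 66.1% for CAD4TB (AUC 0.885) and from 94.8% down to 53.5% for AeoNose (85%/63%).

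**Step 3: effect on the test.** I simulated the exact McNemar test (two-sided 0.05, 1,500 runs, tests independent given disease) with Se_c = 70% and 200 cases, using CAD4TB at AUC 0.885. At a 70% level the difference is +18.0 points and is significant in CAD4TB's favour in 98.7% of runs. At 90% it is −3.9 points and significant against it in 11.7%. At 95% it is −17.9 points and significant against it in 94.6%.

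**Step 4: with the level tied to the comparator.** Each comparison then has one answer.
- Conventional 70%/80% (sensitivity/specificity): CAD4TB (AUC 0.885) 80.4%, +10.4 points; AeoNose (85%/63%) 70.1%, +0.1 points.
- Conventional 60%/85%: CAD4TB 74.6%, +14.6 points; AeoNose 63.0%, +3.0 points.

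**The case against.** The strongest reply is that the phrase is loose rather than wrong. It follows directly on the ROC plan and fixes no number. It does not forbid choosing conventional screening's own specificity, and numerical levels are commonly left to a statistical analysis plan. That stands as far as the missing numbers go, and their absence is not the point here. What remains is the stated rule: levels that are assumed, and several of them, do not describe one observed comparator specificity. Listing levels elsewhere would not cure this unless they were tied to that specificity.

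A second reply is that the single operating point is inferred, because Section 8.1 does not define the comparator. This is fair. Section 3 (Visit 1) records separate symptoms and signs, and Section 6.1.1 includes a graded TBscore. That score, however, is listed only as a measure of clinical severity, and both symptom-based definitions are yes/no. The end-of-visit decision, "either the participant is considered healthy or a presumptive TB case", should not be taken as the comparator: the doctor makes it with the CAD4TB score and the X-ray in hand.

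A reader might infer that the choice of level necessarily decides which tool looks better. The documents do not support that. An assumed conventional point of 75%/85% lies almost exactly on the AUC 0.885 curve (74.6% at 85%), so a reversal around it is built in. With the protocol's 95%/70% pair and the same 75%, the sign does not change anywhere between 70% and 90%.

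A reader might also take this as the trial's central test against existing practice. It is neither listed among the objectives (Section 2) nor among the main endpoints (Section 6.1.2). Section 9.3 says these prisons perform no entry or annual screening, so doctor-led symptom screening of everyone is a study procedure.

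**Conclusion.** The concern holds in a limited form. The comparison as worded does not fit a yes/no comparator and allows sensitivities to be tested at different false-positive rates. The size of the difference then depends on the level chosen: about 22 points for CAD4TB between 70% and 90% specificity with AUC 0.885, and about 14 points with the 95%/70% pair. Its direction may depend on the level too, but that cannot be settled from the documents, which give neither the sensitivity nor the specificity of conventional screening.

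The figures rest on the binormal curve, and the simulated significance rates also on conditional independence. If every chosen level lay on one side of the crossing, the sign would hold but the comparison would still be unmatched. Matching specificity does not address other matters, such as sputum testing being confined to presumptive cases.

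**What to change.** In Section 8.1:

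- Define conventional screening as the doctor's symptom/sign judgement made without chest X-ray or CAD4TB.
- Replace the phrase on assumed levels with: at the device threshold whose specificity equals the observed specificity of conventional screening in the same participants.
- Compare sensitivities by McNemar's test and drop the t-test, since the data are paired yes/no results. Use all TB cases for CAD4TB, which arrives already trained (Section 5.1), and the validation cases for AeoNose.
- Choose the AeoNose threshold from held-out or cross-validated predictions, not from fitted values in the training set. Fitted values would tend to make the device look too specific and spoil the match.
- Report the specificity that each tool achieves, and report paired specificity alongside sensitivity.
- Re-estimate the matched threshold within each bootstrap sample, so that the confidence interval reflects that the threshold is itself estimated.

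The cost is a few sentences, with no new data and no change to study procedures. AeoNose calibration takes place after the end of the study (Section 8.1), so the rule can be fixed before that step. The small downside is that the matched threshold may differ from the one used for triage, so two operating points would be reported.
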